At the end of week 24, patients initially randomized to Treatment B will take 1000 mg extendedrelease ACZ capsules. Similar imaging and clinical evaluations will be performed for the second 24week period. All subjects will discontinue drug at week 48 and obtain a follow-up clinical visit two weeks later. Based upon established pharmacokinetics, the half-life of drug is between 60-75 hours and one would expect insignificant levels within two weeks of discontinuation.

To maintain blinding, patients, evaluating clinicians and MRI analysts will not be informed of treatment assignment or sequence of scans.

We anticipate that sustained increases in regional cerebral perfusion over 6 months will result in improved tissue integrity as measured using diffusion tensor metrics and fewer MS lesions that evolve to persistent black holes.

HYPOTHESIS AND OBJECTIVES

Hypothesis

The underlying hypothesis of this proposal is that long-term therapy with ACZ will improve cerebral perfusion in subjects with MS and this improved perfusion will result in improved tissue integrity in a proportion of MS lesions. To test this hypothesis, subjects will be treated with ACZ, a currently FDA approved agent previously shown in healthy controls to increase cerebral perfusion (Sullivan et al., 1987; Vagal et al., 2009). Subjects will be scanned at various time points (see sections 4 and 6.3) and quantitative MRI metrics will be used to evaluate lesion evolution during and after discontinuation

of treatment.

Primary & Key Secondary Objective

Determine the degree to which divided daily doses of ACZ improves global and regional cerebral perfusion in subjects with MS.

Study subjects will obtain serial MRI scans prior to, during and after therapy (see sections 4 and 6.3). Cerebral blood flow will be measured using an optimized pCASL technique as described by Aslan (Aslan et al., 2010). This will allow us to test the first component of our hypothesis that treatment with ACZ will result in increased regional and/or global perfusion.

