Subjects will receive 1 gram bolus of IV ACZ and a second scan using pCASL sequences will be obtained within 15 minutes of infusion. Subjects will remain in the MRI gantry and receive a third scan to determine CBF at 30 minutes from time of infusion. Subjects will then be removed from the MRI gantry and allowed a break.

Subjects will again be placed on the MRI gantry and scout, 3DT1 and pCASL sequences obtained within 120 minutes from time of ACZ infusion. Subjects will then be removed from the MRI gantry and allowed a break. A final scan will be performed using the same sequences within 240 minutes from time of ACZ infusion.

Stage 1b:

Screening Visit – Subjects will receive a complete medical and neurological examination. In addition, all subjects will obtain CBC, CMP and, if female, urine pregnancy test.

Visit 1 – Subjects will receive non-contrast MRI brain using sequences previously described to ensure proper orientation and registration (scout, 3DT1), sequences necessary for segmentation using MRIAP (2D dual echo, 2D fluid-attenuated inversion recovery [FLAIR]) and pCASL sequences to determine CBF at baseline. Subjects will begin taking 250 mg oral ACZ twice daily and continue for two weeks. Subjects will be encouraged to call the PI with any adverse events (see sections 2.4b and 7.1.2) while on study drug.

Visit 2 – Prior to dose-escalation, subjects will receive non-contrast MRI brain sequences as described above to measure effect of previous oral daily divided dose of ACZ on CBF. Upon completion of MRI, subjects will begin taking 500 mg oral ACZ twice daily and continue for two weeks. Subjects will be encouraged to call the PI with any adverse events (see sections 2.4b and 7.1.2) while on study drug.

Visit 3 – Prior to dose-escalation, subjects will receive non-contrast MRI brain sequences as described above to measure effect of previous oral daily divided dose of ACZ on CBF. Upon completion of MRI, subjects will begin taking 1000 mg oral ACZ twice daily and continue for two weeks. Subjects will be encouraged to call the PI with any adverse events (see sections 2.4b and 7.1.2) while on study drug.

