Visit 4 – Prior to dose-escalation, subjects will receive non-contrast MRI brain sequences as described above to measure effect of previous oral daily divided dose of ACZ on CBF. Upon completion of MRI, subjects will begin taking 1500 mg oral ACZ twice daily and continue for two weeks. Subjects will be encouraged to call the PI with any adverse events (see sections 2.4b and 7.1.2) while on study drug.

Visit 5 – Prior to dose-escalation, subjects will receive non-contrast MRI brain sequences as described above to measure effect of previous oral daily divided dose of ACZ on CBF. Upon completion of MRI, subjects will begin taking 2000 mg oral ACZ twice daily and continue for two weeks. Subjects will be encouraged to call the PI with any adverse events (see sections 2.4b and 7.1.2) while on study drug.

Visit 6 – Subjects will receive non-contrast MRI brain sequences as described above to measure effect of previous oral daily divided dose of ACZ on CBF. Upon completion of MRI, subjects will discontinue use of ACZ.

Stage 2a:

c)

Screening Visit – Subjects will receive a complete medical and neurological examination and obtain screening EDSS evaluation. In addition, all subjects will obtain CBC, CMP and, if female, urine pregnancy test.

Visit 1 – Subjects will receive MRI brain with and without gadolinium contrast utilizing the following sequences in the order listed:

Scout and 3D T1-weighted images to ensure proper orientation and registration 2D dual echo, 3D FLAIR necessary for segmentation

Muti-shell DWI (DTI sequences)

A single shot 2D echo-planar imaging (EPI) for pCASL-based measures of CBF

2D T1-weighted images prior to Gd administration

DSC sequence for measures of CBF, CBV, MTT

2D T1-weighted images after Gd administration

In addition to segmenting MS lesion (T2 hyperintense), we are able to segment T1 pre- and post-Gd lesion volumes. Images obtained at the site at UT are routinely subject to review by a radiologist who is not further involved in image analysis.

Visit 2 – Subjects will receive a complete medical and neurological examination, MSFC & EDSS evaluation as well as patient-reported clinical disability measures (MFIS & MSWS-12) and will be asked questions to ascertain tolerability to daily therapy. All subjects will obtain MRI brain without gadolinium contrast utilizing the sequences described above except for DSC sequence.

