Visit 3 – Subjects will receive a complete medical and neurological examination, MSFC & EDSS evaluation as well as patient-reported clinical disability measures (MFIS & MSWS-12) and will be asked questions to ascertain tolerability to daily therapy. All subjects will obtain MRI brain with and without gadolinium contrast utilizing the sequences described above.

Upon completion of the MRI scan, all subjects will be instructed to discontinue ACZ treatment.

Visit 4 – Subjects will receive a complete medical and neurological examination, MSFC & EDSS evaluation as well as patient-reported clinical disability measures (MFIS & MSWS-12) and will be asked questions to ascertain tolerability to daily therapy. All subjects will obtain MRI brain without gadolinium contrast utilizing the sequences described above except for DSC sequence.

a.

Stage 2b:

Screening Visit – Subjects will receive a complete medical and neurological examination and obtain screening EDSS evaluation. In addition, all subjects will obtain CBC, CMP and, if female, urine pregnancy test.

Visit 1 – Subjects will receive MRI brain with and without gadolinium contrast utilizing the MRI sequences as detailed in Stage 2a.

An MRI scan with the sequences listed above as well as an MSFC & EDSS evaluation by a blinded rater (L.F.) will be obtained prior to treatment to determine baseline values. Patients will also complete subjective disability outcome measures MFIS and MSWS-12. Upon completion of the baseline scan, all subjects will start ACZ therapy and will continue for 24 weeks.

Subjects will be contacted by telephone or email monthly to document tolerability and encouraged to report any AE occurring with drug at any point during the study.

Visit 2 – Subjects will receive a complete medical and neurological examination, MSFC & EDSS evaluation as well as patient-reported clinical disability measures (MFIS & MSWS-12) and will be asked questions to ascertain tolerability to daily therapy. All subjects will obtain MRI brain without gadolinium contrast utilizing the sequences described above except for DSC sequence.

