Visit 3 – Subjects will receive a complete medical and neurological examination, MSFC & EDSS evaluation as well as patient-reported clinical disability measures (MFIS & MSWS-12) and will be asked questions to ascertain tolerability to daily therapy. All subjects will obtain MRI brain with and without gadolinium contrast utilizing the sequences described above.

Visit 4 – Subjects will receive a complete medical and neurological examination, MSFC & EDSS evaluation as well as patient-reported clinical disability measures (MFIS & MSWS-12) and will be asked questions to ascertain tolerability to daily therapy. All subjects will obtain MRI brain without gadolinium contrast utilizing the sequences described above except for DSC sequence.

Visit 5 – Subjects will receive a complete medical and neurological examination, MSFC & EDSS evaluation as well as patient-reported clinical disability measures (MFIS & MSWS-12) and will be asked questions to ascertain tolerability to daily therapy. All subjects will obtain MRI brain with and without gadolinium contrast utilizing the sequences described above.

Upon completion of the MRI scan, all subjects will be instructed to discontinue treatment.

Stage 3: Screening Visits and Procedures

The screening visit will occur within one week of study entry. Subjects with relapsing forms of multiple sclerosis without evidence of other neurologic or cardiovascular disease will be recruited for this study.

Subjects will provide a complete medical history and undergo a complete medical and neurological exam. Blood tests (complete blood counts [CBC] and complete metabolic panel [CMP]) will be obtained from every study subject. Female subjects will also be given a urine pregnancy test during the screening visit. In addition, all subjects will undergo a screening MSFC and EDSS (Kurtzke, 1983).

All subjects will be required to discontinue use of herbal supplements for the duration of the study. Finally, both male and female subjects will be counselled on the use of contraceptive methods (see section 6.2) during the study.

Screening Visit – Subjects will receive a complete medical and neurological examination and obtain screening EDSS evaluation. In addition, all subjects will obtain CBC, CMP and, if female, urine pregnancy test.

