Visit 7 – Subjects will receive a complete medical and neurological examination, MSFC & EDSS evaluation as well as patient-reported clinical disability measures (MFIS & MSWS-12) and will be asked questions to ascertain tolerability to daily therapy. All subjects will obtain MRI brain without gadolinium contrast utilizing the sequences described above except for DSC sequence.

Visit 8 – Subjects will receive a complete medical and neurological examination, MSFC & EDSS evaluation as well as patient-reported clinical disability measures (MFIS & MSWS-12) and will be asked questions to ascertain tolerability to daily therapy. All subjects will obtain MRI brain with and without gadolinium contrast utilizing the sequences described above.

Visit 9 – Subjects will receive a complete medical and neurological examination, MSFC & EDSS evaluation as well as patient-reported clinical disability measures (MFIS & MSWS-12) and will be asked questions to ascertain tolerability to daily therapy. All subjects will obtain MRI brain without gadolinium contrast utilizing the sequences described above except for DSC sequence.

Visit 10 – Subjects will receive a complete medical and neurological examination, MSFC & EDSS evaluation as well as patient-reported clinical disability measures (MFIS & MSWS-12) and will be asked questions to ascertain tolerability to daily therapy. All subjects will obtain MRI brain with and without gadolinium contrast utilizing the sequences described above. Upon completion of the brain MRI, all subjects will be instructed to discontinue assigned treatment.

Visit 11 – Subjects will receive a complete medical and neurological examination, MSFC & EDSS evaluation as well as patient-reported clinical disability measures (MFIS & MSWS-12) and will be asked questions to ascertain any other AEs after discontinuation of therapy. All subjects will obtain MRI brain without gadolinium contrast utilizing the sequences described above except for DSC sequence.

Subjects will be contacted by telephone or email monthly to document tolerability and encouraged to report any AE occurring with drug at any point during the study.

For any part of the study, a subject whose CBC or CMP is not at or near baseline values will repeat these blood tests.

a. Final Study Visit:

The final study visit will be used to document any potential adverse event associated with treatment arm, not previously documented.

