b. Post Study Follow-up and Procedures

Subjects will be referred to their primary care physician for continued monitoring as directed should there be persistent adverse events from use of study drug.

c. Discontinuation Visit and Procedures

Subjects may withdraw from study for any reason and will not be replaced. Subjects who choose to withdraw from the study will be encouraged to complete the end-of-study visit.

Patients with intolerable paraesthesia, change in taste, accelerated change in blood pressure or fluid retention will be withdrawn from the study. Patients with persistent AEs will be referred to their primary care physician for continued monitoring and treatment using standard or care practices.

TRIAL MATERIALS

. Drug Substance: Intravenous Acetazolamide

Package Insert for Intravenous Acetazolamide: AcetaZOLAMIDE for Injection USP

For Intravenous Use.

Rx ONLY.

DESCRIPTION

Acetazolamide, an inhibitor of the enzyme carbonic anhydrase, is a white to faintly yellowish white crystalline, odorless powder, weakly acidic, very slightly soluble in water and slightly soluble in alcohol. The chemical name for acetazolamide is N-(5-Sulfamoyl-1,3,4-thiadiazol-2yl)-acetamide and has the following structural formula: M.W. 222.24 C4H6N4O3S2

Acetazolamide is available for intravenous use, and is supplied as a sterile powder requiring reconstitution. Each vial contains acetazolamide sodium equivalent to 500 mg of acetazolamide. The bulk solution is adjusted to pH 9.6 using sodium hydroxide and, if necessary, hydrochloric acid prior to lyophilization.

CLINICAL PHARMACOLOGY

Acetazolamide is a potent carbonic anhydrase inhibitor, effective in the control of fluid secretion (e.g., some types of glaucoma), in the treatment of certain convulsive disorders (e.g., epilepsy) and in the promotion of diuresis in instances of abnormal fluid retention (e.g., cardiac edema). Acetazolamide is not a mercurial diuretic. Rather, it is a nonbacteriostatic sulfonamide possessing a chemical structure and pharmacological activity distinctly different from the bacteriostatic sulfonamides.

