A comprehensive list of AEs provides previously reported and/or potential AEs associated with ACZ. Common AEs are in **bold**. They include **paresthesias**, particularly a "tingling" feeling in the extremities, hearing dysfunction or tinnitus, loss of appetite, **taste alteration** and gastrointestinal disturbances such as **nausea**, **vomiting**, **dyspepsia and diarrhea**, polyuria, and occasional instances of **drowsiness/fatigue** and confusion. Metabolic acidosis and electrolyte imbalance may occur. Transient myopia has been reported though this condition invariably subsides upon diminution or discontinuance of the medication.

Other occasional adverse reactions include urticaria, melena, hematuria, glycosuria, hepatic insufficiency, flaccid paralysis, photosensitivity and convulsions.

Collecting, Recording and Reporting of Adverse Events

Recording AEs – The treating physician will be the principal investigator ([name]). The treating physician will oversee subject management including all assessments and treatment of adverse events and disease relapses should they occur. The treating physician will make decisions regarding determining relatedness and grading severity of all AEs. The treating physician will be blinded to treatment arm unless necessary to assess safety concern.

Maintaining documentation and reporting AEs – The clinical coordinator ([name]) will assist in subject management, maintain documentation including all subject case report forms (unanticipated problems tracking log) and will submit all reports to the IRB per UTSHC-Houston policy

Safety Monitoring Plan

This pilot study will determine the extent to which improved cerebral perfusion from oral ACZ therapy reduces the evolution of MS lesion into permanent black hole. Subjects will be monitored, as per protocol, by the treating physician for clinical MS activity. However, to our knowledge there are no case reports or other studies to suggest that therapy with ACZ will contribute to new lesion formation or clinical relapse. As such, we do not anticipate an increase in relapse frequency secondary to ACZ.

Subjects will be monitored by the treating physician for AEs and serious AEs (see section 9.1). The frequency and grade of AEs will be documented and treatment arm(s) adjusted or discontinued as needed. Subjects can withdraw consent for study at any point and for any reason during the trial.

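### Stages 1b and 2b schedule no contact after acetazolamide is stopped, so adverse events or abnormal blood results open that day have no planned follow-up

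*Combined protocol and SAP*

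**What the plan says.** **Stages 1b and 2b.** Section 6.3 (Study Visits and Procedures) ends Stage 1b at Visit 6: "Upon completion of MRI, subjects will discontinue use of ACZ". It ends Stage 2b at Visit 5: "Upon completion of the MRI scan, all subjects will be instructed to discontinue treatment". The Trial Schedule tables show no column after Wk 8 in Stage 1b or after Wk 24 in Stage 2b. The Rationale for Study Design also puts the last Stage 1b scan on the day the drug is stopped.

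**Stages 2a and 3.** Stage 2a stops drug at Wk 12 and has Visit 4 at Wk 14. For Stage 3 the Rationale for Study Design says: "All subjects will discontinue drug at week 48 and obtain a follow-up clinical visit two weeks later". At that visit (Visit 11) subjects are "asked questions to ascertain any other AEs after discontinuation of therapy".

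**Adverse event reporting.** At each Stage 1b dosing visit: "Subjects will be encouraged to call the PI with any adverse events (see sections 2.4b and 7.1.2) while on study drug". In Stage 2b, subjects are contacted monthly and "encouraged to report any AE occurring with drug at any point during the study".

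**Repeat tests and referral.** Section 6.3 requires a CBC or CMP that has moved off baseline to be repeated, in any part of the study. Notes under the Stage 2a, 2b and 3 tables add a repeat when transaminases exceed the upper limit of normal or other values change. Neither rule gives a date. Under Post Study Follow-up and Procedures, subjects are referred to primary care "should there be persistent adverse events from use of study drug".

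**The concern.** These are the two open-label stages in which the period after stopping is of most clinical interest. Stage 1b reaches the highest dose in the protocol. Stage 2b is the longest open-label exposure, and its heading in the Rationale for Study Design names long-term safety and tolerability as its purpose. The capsule label reproduced under Trial Materials warns of low sodium, low potassium and metabolic acidosis, and recommends periodic electrolyte checks.

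In both stages the last safety bloods are drawn at the visit where contact ends. If a result is abnormal, or an adverse event is still present, no scheduled contact remains at which the study would learn whether it resolved. What is at stake is the follow-up of individual subjects and the completeness of their safety records. No efficacy conclusion is involved.

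**Working it through.** The plan gives no figure for this point, so the check sets the Trial Schedule tables beside the section 6.3 visit descriptions.

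**Step 1: interval from stop to last scheduled visit** (last visit week minus stop week), and timing of CBC/CMP after the start of dosing.

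| Stage | Stop | Last visit | Interval | CBC/CMP on treatment | CBC/CMP after stop |
|---|---|---|---|---|---|
| 1b | Wk 8 | Wk 8 | 8 − 8 = 0 weeks | Wk 8 only | none |
| 2a | Wk 12 | Wk 14 | 14 − 12 = 2 weeks | Wk 6, 12 | Wk 14 |
| 2b | Wk 24 | Wk 24 | 24 − 24 = 0 weeks | Wk 6, 12, 18, 24 | none |
| 3 | Wk 48 | Wk 50 | 50 − 48 = 2 weeks | every 6 weeks to Wk 48 | none |

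The Stage 1b table has four two-week steps, from 500 to 2000 mg twice daily. Section 6.3 describes five, starting at 250 mg twice daily, which would put the stop at 5 × 2 = 10 weeks. The interval is zero either way.

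**Step 2: Stage 1b bloods.** CBC/CMP is marked at screening and Wk 8 only. The Wk 8 sample is therefore the only scheduled on-drug CBC/CMP, and it is taken at the top dose on the stop day. A separate blood-sample row is marked at every visit, but the protocol does not say what is measured in it.

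**Step 3: do other provisions fill the interval?**
- Monthly contacts (End Points - Safety; section 6.3, Stage 2b) run during the study. Nothing extends them past the stop visit.
- The repeat-test rules apply, but without a deadline and with no later visit to attach them to.
- The Final Study Visit paragraph gives no date. In these two stages the last listed visit is the stop day.
- Referral to primary care passes on the care of a persistent event. It does not return the outcome to the study.
- The DSMB (Safety Monitoring Plan) meets twice a year and can review only what was recorded.

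None of these is a scheduled contact after stopping.

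**Step 4: how many subjects.** Stages 1b and 2b each enrol up to 10, so 10 + 10 = 20, or 10 if Stage 1b is complete. All oral ACZ stages together have 10 + 10 + 10 + 60 = 90 places, and 20/90 = 22%. These are maximum numbers, with a different subject in each place.

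**The case against.** The strongest reply is that the schedules differ because the stages have different purposes. The Stage 2a and Stage 3 visits also take off-drug imaging and clinical measurements, which Stages 1b and 2b may not need. Stage 2a Visit 4 asks about tolerability of daily therapy, so only Stage 3 has an explicit question about events after stopping. History, examination and bloods are all scheduled on the stop day, an abnormal CBC or CMP must already be repeated, and the documents list no ACZ withdrawal reaction. Stage 1b may be finished, since the Stage 2b rationale already names 1000 mg twice daily, although that is an inference. Subjects may also join more than one stage, so some may be seen again.

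Most of this stands. It is why no extra scan, visit or routine test is proposed. It does not supply a date or a contact for closing an event or laboratory result open on the stop day.

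Four stronger readings are tempting, and the documents do not support them:
- **That post-stop event rates will be poorly estimated.** In Stage 3 every subject takes ACZ from Wk 24 to Wk 48. Up to 60 subjects therefore reach Visit 11 after 24 or 48 weeks of drug and are asked the post-stop question. Ten or twenty more subjects would add little. The Stage 3 rationale gives 1000 mg without a frequency, so dose equivalence with Stage 2b is not certain.
- **That Stage 2b restricts reporting to time on drug.** The words "encouraged to report any AE occurring with drug at any point during the study" are repeated directly after Stage 3 Visit 11, when subjects are off drug, so they set no such limit.
- **That the protocol requires myopia to be followed after stopping.** The statement that "this condition invariably subsides upon diminution or discontinuance of the medication" is descriptive and prescribes no follow-up.
- **That lingering drug makes the interval hazardous.** The Stage 3 rationale cites a half-life of 60-75 hours, but the capsule label gives 18 to 24 hours of action on aqueous humor secretion. The point does not depend on either figure.

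**Conclusion.** The concern holds as a minor safety-schedule gap. Stages 1b and 2b end on the stop day with final bloods pending and no later scheduled contact, while Stages 2a and 3 return two weeks later. The gap covers up to 20 subjects, or 10 if Stage 1b has closed, and it exists under either description of the Stage 1b steps. The benefit of closing it is that individual subjects' open events and laboratory results are followed to an outcome. The primary analysis and Stage 3 are unaffected.

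The conclusion assumes that the schedule tables and section 6.3 are complete, and that no post-stop contact is set out in a document outside the protocol.

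**What to change.** In Stage 2b, and in Stage 1b if it is still open:
- Add one telephone or email contact two weeks after the last dose, and show it in the schedule table (Wk 26 in Stage 2b; Wk 10 in Stage 1b on the table's timing).
- At that contact, ask the Stage 3 Visit 11 question about adverse events after discontinuation.
- Record the outcome of every adverse event that was open on the stop day.
- Require any repeat CBC/CMP triggered by the stop-day result to be done by that contact.

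The cost is at most 20 calls or emails, by a method the protocol already uses monthly. The repeat blood test is already required and only gains a deadline. The downside is that each subject closes out two weeks later.
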